14.1.2 Exploratory Endpoints

- Longitudinal measurement of serum markers of bone turnover rate over 6 months
- Measurement of static and dynamic bone parameters summarized in Table 1.

Table 1: Exploratory Endpoints of the Study

Technique	Measurement
Immunohistochemistry:	Osteoblast number and surface Osteoclast number and surface

CONFIDENTIAL

This document is confidential. Do not disclose or use except as authorized.

Micro-CT :	Bone volume fraction Trabecular number Trabecular thickness and separation Connectivity density Structure model index Trabecular bone pattern factor
Nanoindentation :	Elastic modulus
Tetracycline quadruple labeling :	Mineralization lag time Mineral apposition rate Mineral formation rate

14.2 Sample Size/Accrual Rate

Berthold and Haras published a range of normal reference values for the trabecular bone mineral density measured by quantitative CT of the lumbar spine in young adults. In healthy males and females the mean trabecular bone mineral density was 150mg /mL with a standard deviation of 20mg/mL at the start of puberty. In contrast, we expect our patients to be considerably older, to have one or many systemic illnesses, and to have tumors in the sacrum that can compromise bone quality. We expect that mean bone density at the start of the treatment in our population will be considerably lower. Assuming that it's at least 1 standard deviation less that of a normal young adult, we get an estimate of 130mg/dL at the start of treatment in all study patients. It is likely that our population will exhibit significant differences by sex owing to bone density being more affected by age in females than in males. In absence of prior studies, it is very difficult to estimate this difference. In fact, the purpose of this pilot study is in part to provide some numerical data to help guide future studies. At present, we must carry our sample size calculations keeping in mind these potential pitfalls.

The “event of interest” in this study is a change in trabecular bone density. Our hypothesis is that radiation induces loss of trabecular bone density in surgical and non-surgical patients. We would like to be able to detect a change in the average bone density of 10 mg/mL (approximately 5%) before and after radiation treatment. Assuming the standard deviation of the change we hope to observe is 15mg/dL, we get the following estimates.

Size = 30, Power = 0.942, alpha = 0.05
 Size = 20, Power = 0.807, alpha = 0.05
 Size = 10, Power = 0.469, alpha = 0.05

The main treatment arm in our patient population is the surgical patients. We plan to enroll 20 surgical patients given the results of the power analysis. The purpose of the non-surgical arm is to serve as a control for any confounding effects due to surgery. We plan to enroll 10 non-surgical patients. Smaller sample size significantly reduces the power of our analysis in the non-surgical arm. However, given that the vast majority of our patients receive surgery, the time it would take to enroll 20 patients into the non-surgical arm would undermine the purpose of doing an exploratory study to begin with.

The Kolmogorov–Smirnov test on the normality of the distribution of bone mineral density and trabecular bone mineral density values will be carried out in each group. To evaluate the effects of radiation, we will

CONFIDENTIAL

This document is confidential. Do not disclose or use except as authorized.

use the Student t-test and Mann–Whitney test to compare the results from the iliac crest and the sacrum. We will use the Cox stratified model to identify confounding factors.

We plan to enroll 1-2 subjects per month. Subject enrollment is limited by patient availability.

The estimated study accrual by gender, race and ethnicity is shown in the table below.

Accrual Targets				
Ethnic Category	Sex/Gender			
	Females		Males	Total
Hispanic or Latino	1	+	0	= 1
Not Hispanic or Latino	14	+	15	= 29
Ethnic Category: Total of all subjects	15	+	15	= 30
Racial Category				
American Indian or Alaskan Native	0	+	0	= 0
Asian	0	+	0	= 0
Black or African American	1	+	1	= 2
Native Hawaiian or other Pacific Islander	0	+	0	= 0
White	14	+	14	= 28
Racial Category: Total of all subjects	15	+	15	= 30

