Most MGH patients with sacral tumors are treated with combination of surgery and adjuvant radiation. They receive 50.4 Gy of photon/proton beam radiation before surgery, in accordance with the protocol summarized in Figure 9 (A). After the tumor is surgically removed, patients receive another 19.8 Gy of radiation, for a total dose of 70.2 Gy. We plan to enroll 20 patients treated in this fashion into the “Surgical Arm” of the study. It has been previously suggested that in patients treated with combination of surgery and radiation, the high rate of sacral fractures may be partially attributable to surgery. Yet, sacral fractures have been reported in patients who were treated with radiation alone. There is no data to date that can account for these observations. To explore this question, we plan to enroll 10 patients treated with radiation alone into the “Non-surgical Arm” of our study. These patients receive between 72 Gy

CONFIDENTIAL

This document is confidential. Do not disclose or use except as authorized.

(osteosarcoma and chondrosarcoma) to 77.4 Gy (for chordoma) of radiation over the course of 7 to 8.5 weeks, as outlined in Figure 9 (B).

The long term goal of this research is to improve treatment outcomes and quality of life in patients with tumors of any origin, who undergo treatment with radiation. We hope that the results of this translational research may ultimately enable the predication of patients at risk of fracture and allow intervention before fracture occurs.

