8. CORRELATIVE/SPECIAL STUDIES

8.1 **Pharmacokinetic Studies**

N/A

8.2 **Pharmacodynamic Studies**

N/A

8.3 **Special Studies**

8.3.1 *Blood Draws*

We will follow the trends in serological markers over a 6 month period beginning prior to the first dose or radiation received by the patient. The study Schema outlines specific time points when we plan to draw

CONFIDENTIAL

This document is confidential. Do not disclose or use except as authorized.

the blood samples. After all studies have been performed we will label the samples with a code. The key to the code will connect the sample with the subjects health information. The key to the code will be kept in a password protected computer of the principal investigator. Samples will be stored at the BioBank and Research Laboratory Services for the Maine Medical Center Research Institute.

Figure 10

What is measured:

- N-Telopeptide (NTX)
- Serum tartrate-resistant acid phosphatase 5b (TRAP5b)
- Osteocalcin (OC)
- Type 1 procollagen N-terminal (P1NP).
- PTH
- Calcium as part of a standard metabolic panel
- Phosphate

8.3.2 *Quantitative CT Scans*

Patients in both arms of the study will undergo two QCT scans. First QCT will be done at Day 1, prior to initiation of radiation treatment. Patients in the Non-Surgical Arm will undergo a second QCT at six months after their first radiation treatment. In contrast, patients in the Surgical Arm will undergo their second QCT immediately prior to surgery, 10 weeks after the first scan. Once the spinal instrumentation is introduced during the surgery, it renders the analysis impossible due to artifact. Scans will be performed by the MGH Musculoskeletal Imaging Research Core (MIRC) under the direction of [name] (Radiology). We will use the QCT Pro protocol, detailed in Section 6.1.3 – Radiation Exposure Risks. Volumetric QCT of L1, L2 and S1 vertebrae will be obtained. Images will be saved in standard DICOM format and transferred to a PACS workstation for analysis.

What is measured:

- Trabecular bone mineral density (Tb. BMD)

8.3.3 *Bone Biopsies*

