9. STUDY CALENDAR

9.1.1 Non-Surgical Arm Study Calendar

Time point	Visit 1	Visit 2	Visit 3	Visit 4	Visit 5	Final visit
	Screening	Start RT Baseline	Halfway RT ~3.5 Weeks	End of RT ~7 Weeks	~3Months after RT	~6 Months after RT
Medical History	X					
Study Blood test		X	X	X	X	X
CT scan		X			X	
Pregnancy Test	X					

RT = radiotherapy

* Study visit are dependent on treatment events like start/end of pre- or post-op radiotherapy and surgery. Therefore treatment delay will result in delay of study visits.

CONFIDENTIAL

This document is confidential. Do not disclose or use except as authorized.

9.1.2 *Surgical Arm Study Calendar*

	Visit 1	Visit 2	Visit 3	Visit 4	Visit 5	Visit 6	Visit 7	Visit 8	Final Visit
	Before Surgery				Surgery Week		After post-op RT	Follow-Up	
	Screening	Start RT Baseline	End RT ~5.5 Weeks	3-5 days before surgery	Surgery stage 1	Surgery stage 2	End post-op RT	1 month after post-op RT	4 months after post-op RT
Medical History	X								
Eligibility blood test	X								
CT scan		X		X					
Study Blood test		X	X				X	X	X
Bone Biopsy					X	X			
Dispense drugs	X		X						
Pregnancy Test	X								

RT = radiotherapy

* Cycle 1 drugs will be taken between visit 1 and 2. Cycle 2 drugs will be taken between visit 3 and 4*
 Study visit are dependent on treatment events like start/end of pre- or post-op radiotherapy and surgery.
 Therefore treatment delay will result in delay of study visits.

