14.1.1 Primary Endpoint

- *Outcome of interest:* change in trabecular bone mineral density (Tb. BMD) measured by QCT of the lumbar spine at the start and at the end of radiation treatment

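### The non-surgical arm is justified as a control for surgery, but both surgical-arm QCT scans come before surgery, so the primary Tb. BMD measure carries no information on surgery

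*Combined protocol and SAP*

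**What the plan says.** **Purpose of the arm.** Section 14.2 states: "The purpose of the non-surgical arm is to serve as a control for any confounding effects due to surgery". The only outcome sized in that section is change in Tb. BMD. Section 2.1 gives the background: it has been suggested that "the high rate of sacral fractures may be partially attributable to surgery", yet fractures also occur after radiation alone. It continues: "To explore this question, we plan to enroll 10 patients treated with radiation alone into the" non-surgical arm. The question in 2.1 is therefore about fractures.

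**Primary endpoint.** Section 14.1.1 defines it as change in Tb. BMD measured by "QCT of the lumbar spine at the start and at the end of radiation treatment".

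**Scan schedule.** For both arms, 8.3.2 says: "First QCT will be done at Day 1, prior to initiation of radiation treatment". It then says that "patients in the Surgical Arm will undergo their second QCT immediately prior to surgery, 10 weeks after the first scan", and gives the reason: "Once the spinal instrumentation is introduced during the surgery, it renders the analysis impossible due to artifact". Calendar 9.1.2 agrees. It shows CT at Visit 2 (start of radiotherapy) and at Visit 4, "3-5 days before surgery", and none afterwards. The non-surgical second scan is at six months after first radiation in 8.3.2, but at about 3 months after the end of radiotherapy in calendar 9.1.1.

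**Treatment.** Under section 5 the treating physician decides the treatment. Surgical candidates receive 50.4 Gy before surgery and a further 19.8 to 27 Gy after it. Non-surgical patients receive 72 to 77.4 Gy according to histology. Section 5.2 gives labeling drugs to the surgical arm only.

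**The concern.** A control arm informs about an exposure only if one group has had that exposure when the outcome is measured. For QCT, neither group has. The reason that 14.2 gives for enrolling these ten patients therefore cannot be met on the endpoint that the section is about.

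What is at stake is interpretation. Read with the stated purpose in mind, an arm difference in Tb. BMD change invites the conclusion that surgery affects bone density, and no difference invites the conclusion that it does not. Neither would be supported. Section 14.2 says the pilot is partly meant to supply numbers for later studies, so a misattributed contrast could be carried forward.

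**Working it through.** **1. The plan's own figures.** Inputs from 14.2: change to detect 10 mg/mL; SD of change 15 (printed as mg/dL, taken here as mg/mL); alpha 0.05. For a two-sided paired t-test, d = 10/15 = 0.667, noncentrality = d × √n, df = n − 1.

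| n | Noncentrality | Power, recomputed | Power, stated |
|---|---|---|---|
| 30 | 3.65 | 0.942 | 0.942 |
| 20 | 2.98 | 0.807 | 0.807 |
| 10 | 2.11 | 0.469 | 0.469 |

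The figures reproduce. They are powers for before/after change within patients and say nothing about surgical versus non-surgical.

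**2. Exposure to surgery at each measurement.**

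| | Surgical arm | Non-surgical arm |
|---|---|---|
| First QCT | Day 1, before radiation | Day 1, before radiation |
| Second QCT | 10 weeks, before surgery | after radiation, no surgery |
| Had study surgery by second QCT | 0 of 20 | 0 of 10 |
| QCT after surgery | none | not applicable |

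Biopsies (8.3.3) are taken in the surgical arm only, so they give no arm comparison either.

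**3. What does differ at the second scan.**

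- Prescribed dose received: 72 − 50.4 = 21.6 Gy and 77.4 − 50.4 = 27.0 Gy more in the non-surgical arm, or 1.43 to 1.54 times as much. These are prescribed doses; the dose at the scanned vertebrae is not given.
- Time from first scan: 10 weeks in the surgical arm. In the non-surgical arm it is about 26 weeks under 8.3.2, or about 7 + 13 = 20 weeks under calendar 9.1.1. The gap is 26 − 10 = 16 weeks or 20 − 10 = 10 weeks.
- Allocation by the treating physician, with histology setting the non-surgical dose.
- Labeling drugs in the surgical arm only.

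Section 14 names no adjustment for dose or scan time. The stratified Cox model in 14.2 lists no covariates and is not tied to Tb. BMD.

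**4. Illustration of size (assumptions, not plan figures).** If loss were proportional to prescribed dose and equal to 10 mg/mL at 50.4 Gy, dose alone would give an arm difference of 10 × (72/50.4 − 1) = 4.3 to 10 × (77.4/50.4 − 1) = 5.4 mg/mL, with no surgery effect. Chance is larger still. With SD 15 in both arms, SE = 15 × √(1/10 + 1/20) = 5.81 and t(0.975, 28 df) = 2.05, so the 95% CI half-width is about 11.9 mg/mL. A two-sample t-test of 20 against 10 would have 38% power for a 10 mg/mL difference and would need about 17 mg/mL for 80%.

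**5. Whether 14.1.1 rescues the comparison.** Read as the end of all radiation, its second time point falls after surgery in the surgical arm, where no QCT is scheduled and 8.3.2 says none could be analysed. Read as the end of pre-operative radiation, it is about 5.5 weeks, whereas the scan is at 10 weeks. In the non-surgical arm radiation ends at about 7 weeks and the scan is at about 20 or 26. Neither reading matches the schedule, and neither yields a usable post-operative scan.

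**The case against.** The strongest reply has four parts.

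*The sentence in 14.2 does not mention QCT, and 2.1 asks about fractures.* This stands as a limit on scope. Fracture is followed for 12 months (5.7), and bloods are drawn in both arms, after surgery in the surgical arm. By then that arm's total is 50.4 + 19.8 = 70.2 to 50.4 + 27 = 77.4 Gy, close to 72 to 77.4 Gy. A reader might infer that the non-surgical arm can say nothing about surgery at all; the documents do not support that. But 14.2 makes its statement while sizing Tb. BMD, so the correction belongs there.

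*No between-arm test of Tb. BMD change is planned.* This is correct. The hypothesis is loss in each kind of patient, the powers are within-patient, and the group comparison in 14.4 concerns PROMIS scores. A reader might infer that the plan commits the trial to a false conclusion about surgery. It does not: the risk lies in interpretation, and such a conclusion would be unsupported rather than shown to be false. Still, a control has meaning only through comparison; if none is intended on QCT, the sentence should not imply one.

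*Scanning before surgery protects the primary question.* This also stands. It keeps surgery out of the radiation-effect measure, which means that QCT needs no surgery control.

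*This is a small pilot that admits low power in this arm.* That excuses imprecision. It does not supply an exposure that is absent from both arms.

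**Conclusion.** The point holds for QCT. The primary measure contains no information on surgery in either arm, because both surgical-arm scans precede the operation. Any arm difference in Tb. BMD change reflects a 21.6 to 27.0 Gy gap in prescribed dose, a 10 to 16 week gap in scan timing, patient selection, labeling drugs in one arm only, and chance. It does not reflect surgery. A reader might reduce this list to dose and time; that is too narrow, since treatment is not randomised and the arms are small.

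The finding rests on the text of 8.3.2 and calendar 9.1.2, which agree on the surgical-arm schedule, and needs no outside figure. The mg/mL values under the illustration depend on the assumptions stated there and are not needed for the conclusion. A reader might also infer that the primary result is compromised. It is not: the within-arm radiation analysis and its sample size are untouched. Severity is should-fix, because the correction changes what may be concluded but no scan, test or patient number.

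**What to change.** - **14.2:** replace the surgery-control sentence. State that the non-surgical arm is a separate radiation-only cohort, that Tb. BMD change is analysed within each arm, and that no QCT arm difference, or absence of one, will be attributed to surgery.
- **2.1 and 14.2:** limit the surgery question to outcomes collected in both arms that in the surgical arm fall after surgery, namely fracture follow-up and post-radiotherapy serum markers. Label it descriptive, because the arms are not randomised and the later blood draws differ in time (about 3 and 6 months after radiotherapy against 1 and 4 months). Fracture is not among the endpoints in 14.1, so it should be listed there if it is to be reported this way.
- **Reconcile:** the second time point in 14.1.1 with 8.3.2, and the non-surgical second-scan time in 8.3.2 with calendar 9.1.1.

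The cost is an amendment to wording. It needs no extra patients, scans or visits. The sponsor gives up only a claim that QCT under this schedule cannot support.

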5.7 Duration of Follow Up

Participants will be followed for radiographic and/or clinical evidence of fracture and assessment of quality of life for 12 months after their surgery/radiotherapy or until death, whichever occurs first. Participants removed from study for unacceptable adverse events will be followed until resolution or stabilization of the adverse event.

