Bone biopsies will be performed on patients enrolled in the Surgical Arm of the study. Each patient will undergo two biopsies. At the time of each biopsy we plan to collect two bone samples. Figure 10 shows the location of the planned biopsy sites. The first biopsy (the control) will be taken from the iliac wing of the pelvis. This area lies outside of the radiated field, and will serve as a normal bone control. The second biopsy will be taken from the irradiated part of the sacrum. Bone biopsies will be evaluated for the end points of dynamic histomorphometry, and possible radiation-induced woven bone and bone mineralization abnormalities. Micro-CT will be performed on half of the bone samples prior to embedding to evaluate 3D trabecular microstructure. Biopsies that will be used for dynamic histomorphometry will be stored in 10% buffered formalin at room temperature in a dark space. We will send the biopsies to [name] at Columbia University for analysis. Transfers will be done in batches using FedEx. After all studies have been performed we will label the biopsies with a code. The key to the code will connect the biopsy with the subjects health information. The key to the code will be kept in a password protected computer of the principal investigator. Biopsies will be stored either at room

[figure not shown]
CONFIDENTIAL

This document is confidential. Do not disclose or use except as authorized.

temperature (embedded specimen) or frozen (fresh specimen) at the Endocrine Unit Research Laboratory of the Massachusetts General Hospital.

Figure 10 shows the location of two biopsy sites.

Figure 10: Location of the Planned Bone Biopsy Sites.

Biopsies will be done at the time of the scheduled tumor surgery. Sacral tumors are removed in stages. The first stage is done via anterior exposure, allowing access to the iliac crest. We will collect these samples first. Using a 7,5mm Rochester trephine two bone samples will be removed from the superior apex of the iliac wing in the midline (as defined as a point midway between the anterior superior and posterior superior iliac crests). In most cases, the biopsy site will be accessible through the incision made for the anterior approach. However, in those rare cases when the biopsy site is not accessible via the incision made as part of the standard of care, then a separate small incision (at most 3 cm long) will have to be made.

[figure not shown]

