14. STATISTICAL CONSIDERATIONS

14.1 Study Design/Endpoints

We will have two groups of patients, those treated with radiation alone, and combination of surgery and radiation. Figure 13 summarizes the proposed enrollment groups for this study, depending on the type of treatment patients are undergoing.

Figure 13: Proposed Subject Enrollment Plan

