14.3 Stratification Factors

Patients will be stratified by the type of treatment they are undergoing (surgical vs. non-surgical).

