14.4 Analysis of Secondary Endpoints

Paired t-test and Wilcoxon signed-rank test will be performed on the differences between the two groups in the average values of PROMIS T scores. A P-value of 0.05 will be considered to be statistically significant. Spearman and Kendall rank correlations will be used to measure the strength of dependence between the bone mineral density and exploratory variables whenever possible.

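### Section 14.2 names an unpaired rank test for iliac and sacral samples from the same patients, while Section 14.4 names paired tests for two groups of different patients

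*Combined protocol and SAP*

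**What the plan says.** **Biopsies.** Section 8.3.3 biopsies the surgical arm only: "Each patient will undergo two biopsies. At the time of each biopsy we plan to collect two bone samples". The first biopsy is an iliac control from outside the radiation field and the second is from the irradiated sacrum. Section 14.2 then plans to "use the Student t-test and Mann–Whitney test to compare the results from the iliac crest and the sacrum".

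**PROMIS.** Section 14.4 states: "Paired t-test and Wilcoxon signed-rank test will be performed on the differences between the two groups in the average values of PROMIS T scores". That section does not define the two groups. Section 14.1 does: "We will have two groups of patients, those treated with radiation alone, and combination of surgery and radiation". Section 14.3 stratifies on the same split, and Section 14.2 plans 20 surgical patients and adds "We plan to enroll 10 non-surgical patients". Section 5.7 provides for "assessment of quality of life for 12 months after their surgery/radiotherapy or until death", but neither calendar in Section 9 has a row for PROMIS or quality of life.

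**Power.** Section 14.2 gives power for the QCT change at three sizes. The line for the surgical arm is "Size = 20, Power = 0.807, alpha = 0.05".

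**The concern.** The tests do not fit the data structure in either place. Iliac and sacral values come from the same person, so the natural unit is the within-patient difference, yet Mann–Whitney treats the two sites as independent samples. The term Student t-test leaves pairing open. The PROMIS comparison, read with the only groups the plan defines, sets different people against each other in unequal numbers, so neither a paired t-test nor a signed-rank test can be computed. The two sets of tests look as if they were interchanged, though that is an inference.

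The iliac–sacrum contrast is the only between-site test named for the biopsy measures, which serve secondary objectives 1.3.2 to 1.3.4. With 20 patients there is little information to spare, and a test that ignores the matching does not in general run at its stated 0.05 level.

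**Working it through.** **1. Reproduce the plan's own power.** Inputs from Section 14.2: change 10, SD of the change 15, alpha 0.05. Section 14.2 prints the SD in mg/dL and the change in mg/mL; both are taken as mg/mL. Sidedness is not stated; two-sided is assumed.

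Paired t-test: noncentrality (10/15)·√n, degrees of freedom n − 1. At n = 20 the noncentrality is 0.667 × 4.472 = 2.98.

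| n | Printed | Paired t, two-sided | Two-sample t, n per group |
|---|---|---|---|
| 30 | 0.942 | 0.942 | 0.719 |
| 20 | 0.807 | 0.807 | 0.538 |
| 10 | 0.469 | 0.469 | 0.292 |

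The printed figures are a two-sided paired calculation. A within-patient t-test may therefore be meant for the biopsies too, but Section 14.2 does not say so, and this cannot rescue Mann–Whitney.

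**2. Effect of ignoring the matching.** Let σ be the SD at each site and ρ the within-patient correlation. The mean difference over n patients has variance 2σ²(1 − ρ)/n. An independent-samples test uses 2σ²/n. It therefore overstates the variance when ρ > 0, is right when ρ = 0, and understates it when ρ < 0.

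**3. Size.** Setting: 20 pairs, one value per site, bivariate normal, σ = 1, two-sided 0.05, difference 10/15 = 0.667 SD. The difference is borrowed from the QCT calculation for scale only, and ρ is assumed because the documents give none. The t-tests used 400,000 simulated trials and the rank tests 200,000. The paired t power also follows from noncentrality 0.667·√20/√(2(1 − ρ)), for example 2.98/√1 = 2.98 at ρ = 0.5, which gives 0.807.

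| ρ | Mann–Whitney power | Signed-rank power | Unpaired t power | Paired t power | Mann–Whitney type I | Unpaired t type I |
|---|---|---|---|---|---|---|
| −0.3 | 0.512 | 0.399 | 0.535 | 0.419 | 0.082 | 0.084 |
| 0 | 0.515 | 0.496 | 0.538 | 0.517 | 0.049 | 0.050 |
| 0.2 | 0.514 | 0.584 | 0.543 | 0.609 | 0.030 | 0.030 |
| 0.5 | 0.525 | 0.787 | 0.553 | 0.807 | 0.008 | 0.008 |
| 0.7 | 0.539 | 0.944 | 0.569 | 0.954 | 0.001 | 0.001 |

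The paired tests hold type I error at 0.048 to 0.050 throughout. The apparent power advantage of the unpaired tests at ρ = −0.3 comes with a type I error above 0.05. The mean confidence interval from the unpaired t is 0.97, 1.09 and 1.37 times as wide as the paired one at ρ = 0, 0.2 and 0.5.

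**4. Other scaling.** If the SD of the paired difference is held at 15 and ρ varies, paired t power stays at 0.81 and signed-rank at about 0.79. Mann–Whitney power is then 0.81, 0.68, 0.53 and 0.27 at ρ = 0, 0.3, 0.5 and 0.7. The direction is the same.

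**5. PROMIS.** With 20 and 10 different patients, a paired test has no pairs. The two-sample t-test has noncentrality d·√(20 × 10/30) = 2.58d on 28 degrees of freedom. Its power is 0.24, 0.51 and 0.70 at assumed standardised differences of 0.5, 0.8 and 1.0.

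**The case against.** Several points can be made for the plan.

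- *Student t-test can mean a paired test.* It can, and the printed powers suggest the planners think in paired terms. Only Mann–Whitney is mismatched beyond doubt in Section 14.2.
- *The loss rests on an unknown correlation.* This stands. At zero correlation nothing is lost. Sections 2.4.3 and 8.3.8 stress how much histomorphometric values vary between sites, which gives no support to the higher values, and nothing in the documents suggests a negative one. The figures show a range and do not estimate the loss in this trial.
- *The stakes are low.* This is a pilot, Section 14.1.2 lists these measures as exploratory, and no sample size or decision rule depends on them. For the dynamic measures, the patient's own pretreatment label set is also an intended control. This limits the weight of the point but does not make the named tests fit.
- *PROMIS may be a leftover.* It appears in no objective and no endpoint list. However, Section 5.7 still plans 12 months of quality-of-life assessment, and Section 14.4 still names tests. The contents page lists a survey appendix that is absent from the copy reviewed; nothing is inferred from that.
- *A within-patient PROMIS change may be meant.* Paired tests would then be right, but the sentence speaks of two groups and gives no time points.

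**Conclusion.** The concern holds. Mann–Whitney is the wrong test for iliac versus sacrum, the t-test there needs to be stated as paired, and the PROMIS tests cannot be run between the arms as worded. No other section corrects either sentence.

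Under the illustrative setting, Mann–Whitney gives up about 0.07 of power at correlation 0.2 (0.584 − 0.514) and about 0.26 at 0.5 (0.787 − 0.525), and essentially nothing at 0. At positive correlation the error is conservative. These sizes rest on the assumed correlation, the borrowed effect size and normality. The mismatch itself rests on none of them. The point should be fixed, but it does not touch the primary endpoint or its sample size.

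**What to change.** - **Section 14.2:** for iliac versus sacrum, specify a paired t-test on one iliac-minus-sacral difference per patient, with the Wilcoxon signed-rank test as sensitivity analysis. If a site yields more than one value, average within site first. This is valid at any correlation.
- **Section 14.4:** for PROMIS between arms, specify a Welch t-test or Mann–Whitney test. If a within-patient change is meant, say so and name the two time points.
- **Section 9:** add the PROMIS assessment times to both calendars.
- **Optional:** name the paired contrast of the two label sets within the sacral core for mineral apposition and formation rates, which Sections 2.4.3 and 8.3.8 already intend.

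The cost is wording in two sections and one row in each of two calendars, with no new patients, samples or labels. The calendars end about 6 months after radiotherapy (non-surgical arm) and 4 months after postoperative radiotherapy (surgical arm). Covering the 12 months in Section 5.7 may therefore need a contact after the final visit.
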